### Human Studies of Anesthesia

In recent years, aided largely by non-invasive imaging methods, significant progress has been made in understanding systems-level anesthetic effects in humans. General anesthetic drugs dramatically reduce or increase (unique to ketamine) cerebral metabolism and blood flow globally across the brain. This is consistent with our understanding that general anesthetic drugs act at multiple sites throughout the brain. Stimulus-induced activity in primary cortical areas decreases under anesthesia, as does functional connectivity, though some degree of resting state connectivity has been shown to persist. Ascending arousal systems spanning the brainstem, thalamic and cortical networks appear to become active during emergence from anesthesia-induced unconsciousness. Disruption of anterior-posterior cortico-cortical connectivity has been proposed as a common mechanism to explain these diverse findings. However, there is also considerable evidence to support thalamocortical and subcortical mechanisms as well.

The neurophysiological mechanisms underlying these observed changes in brain metabolism and functional connectivity remain unclear. However, anesthetic drugs are known to produce large stereotyped oscillations that may explain these brain metabolism and functional connectivity changes. To bridge the gap between observed changes in brain metabolism and fMRI-derived functional connectivity, it is essential to conduct studies that can simultaneously observe fast time-scale neurophysiological dynamics across multiple functionally-connected brain regions. To understand how neurophysiology relates to time-varying states of altered arousal requires detailed behavioral characterizations. Although it is clear that unresponsiveness is not necessarily unconsciousness, behavioral responses nonetheless provide crucial information on the state of altered arousal. Most of the aforementioned work has been performed in propofol or inhaled anesthetics, and studies of ketamine are clearly needed.

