## 2. SPECIFIC AIMS

**AIM 1:** To use high-density EEG recordings to characterize the different brain states induced by ketamine

**Hypothesis 1.1.** Ketamine gamma-burst pattern will be associated with a zero probability of response to auditory stimuli

**Hypothesis 1.2.** Ketamine gamma-stable pattern consists of two distinct brain states: an anesthetic state with zero probability of response to auditory stimuli and a hallucinatory state with non-zero probability of response to auditory stimuli

**AIM 2:** To use high-density EEG recordings to characterize oscillatory dynamics associated with the analgesic effect of ketamine

**Hypothesis 2.1.** Ketamine theta power will correlate with analgesia

**Hypothesis 2.2.** Ketamine gamma power will not correlate with analgesia

**AIM 3:** To use inflammatory profiling of serum to understand the effect of ketamine on systemic inflammation

**Hypothesis 3.1.** Ketamine-anesthesia will be associated with decreased levels of pro-inflammatory cytokines interleukin 6 and TNF-alpha

**Hypothesis 3.2.** Levels of pro-inflammatory cytokines interleukin 6 and TNF-alpha will correlate with a decrease in perception of painful stimuli

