**Study Visit:** During the study, a board-certified anesthesiologist will be present whose sole responsibility will be to monitor (check) your safety. The sequence of this study visit will be as follows: arrival (approximately 45 minutes), baseline (approximately 15 minutes), loss of consciousness (approximately 15 minutes), recovery of consciousness (approximately 60 minutes), and discharge (approximately 45 minutes). We anticipate the study to last approximately 3 to 5 hours.

**A. Arrival:** Confirmation of the study subjects' fasting status (minimum 8 hours) will be made. A urine sample will be obtained for pregnancy testing in all female study subjects. The following assessments will be performed: 1.) Clinician Administered Dissociative States Scale (CADSS) to assess for hallucinations; 2.) Promis Item Bank v.1.0 – Emotional Distress-Anxiety Short Form 8A modified to ask for symptoms experienced within the past hour; 3.) Promis Item Bank v.1.0 – Meaning and purpose Short Form 8A; and, 4.) Promis Item Bank v.1.0 – Positive Affect Short Form 15A (modified to ask for symptoms experienced within the past hour). The following computer presented neurocognitive assessment tests will also be performed: Global Precedence, Operation Span and Columbia Card tasks will also be administered (<https://www.neurobs.com>).

Standard monitors for anesthesia care monitoring including blood pressure (cuff), electrocardiogram, capnography and pulse oximetry and a 64-channel EEG montage will be placed on the subject. Video of the study subject may be recorded during baseline, induction and recovery from hypnosis periods to assess the study subject's level of arousal. Permission to record video for data analysis purposes will be obtained from the research consent form. An intravenous line will be placed for drug administration, and we will obtain approximately 15ml of blood (baseline pre-ketamine).

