During this period, a calibrated cuff pain stimuli will be delivered to the gastrocnemius area of the lower leg using a validated cuff pain device (Hokanson Rapid Cuff Inflator), titrated to 8-9/10 pain. One advantage of using cuff algometry pain is that, unlike more superficial methods (e.g. heat pain), cuff pain responses are unaffected by sensitization or desensitization of the skin. The following questionnaires will be administered to assess pain intensity and quality: 1) PROMIS Numeric Rating Scale V1.0 – Pain Intensity 1A; 2) PROMIS Scale v2.0 – Neuropathic Pain Quality 5a; and, 3) PROMIS Scale v2.0 – Nociceptive Pain Quality 5a. Participants will be oriented to the following pain scale: (1) 0-1 out of 10 as “tolerable”; (2) 2-3 out of 10 as “slight discomfort”; (3) 4-7 out of 10 as “moderate discomfort”; (4) 8-9 out of 10 as “painful”; and (5) 10 as “maximum pain”.

**B. Baseline:** A 10 to 15-minute period of EEG recording will be obtained for EEG calibration (i.e. eye movements, eye blinks, facial muscle movement) and EEG normalization (awake-eyes closed). Recordings of physiological measurements (blood pressure, heart rate, pulse oximetry, end-tidal carbon dioxide, electrooculogram, electromyogram and galvanic skin response) will be initiated and maintained from the beginning of the study protocol until the subject is ready for discharge.

**C. Loss consciousness:** 2mg/kg of ketamine will be infused (Medfusion pump) over approximately 5 minutes to gradually induce and allow for rapid emergence from ketamine-anesthesia. This anesthetic dose is expected to cause approximately 10-15 minutes of loss of consciousness/responsiveness. Subjects will be asked to respond to auditory stimuli via button-press jittered at random between 4 and 8 second intervals in order to resolve the precise period at which loss and recovery of consciousness/responsiveness occurred at a fine temporal scale.

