anesthesiologist may be required to administer intravenous labetalol 5 to 20 mg IV push over approximately 2 minutes for three blood pressure readings greater than 160/100. Blood pressure readings will be obtained 3-5 minutes apart. Intravenous glycopyrrolate in 0.1mg increments may also be administered for excessive salivary secretion. In order to minimize external stimuli, ketamine administration will occur in a room with low lighting and minimal noise. Based on the acuity of physiological or behavioral changes, the anesthesiologist may modify these treatment recommendations.

The study investigator will be available over the phone at anytime to address any concerns. Subjects will be advised to contact the study PI for any medical related concerns. The study PI may advise subjects to obtain follow-up care from their nearest emergency department or primary care physician. Study staff will use the EPIC alert system to monitor subject admittance to any Partners Hospital. The study investigator will contact all study subjects 24 hours after completion of the study visit to address any concerns or study related adverse effects.

**D. Recovery of consciousness:** We will conduct assessments 5-minutes after recovery of consciousness and at approximately 15-minute intervals after recovery of consciousness for a total of three assessments. These assessments will consist of: 1.) CADSS; 2.) Promis Item Bank v.1.0 – Emotional Distress-Anxiety Short Form 8A modified to ask for symptoms experienced within the past hour; 3.) Promis Item Bank v.1.0 – Meaning and Purpose Short Form 8A; and, 4.) Promis Item Bank v.1.0 – Positive Affect Short Form 15A (modified to ask for symptoms experienced within the past hour. After these assessments, the cuff pain device will be inflated (pre-calibrated pressure; see Arrival subsection above), and pain intensity and quality assessments will consist of: 1.) PROMIS Numeric Rating Scale V1.0 – Pain Intensity 1A; 2.) PROMIS Scale v2.0 – Neuropathic Pain Quality 5a; and, 3.) PROMIS Scale v2.0 – Nociceptive Pain Quality 5a.

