After the third assessment (i.e. approximately 35 minutes after recovery of consciousness), we will administer 0.05 mg/kg of midazolam (maximum dose of 4 mg) to resolve ketamine-induced perceptual disturbances. Midazolam is routinely administered during the peri-operative period to mitigate ketamine-induced perceptual disturbances. Approximately 5 minutes after midazolam is administered, we will resume assessments for a minimum of two assessments (approximately 55 minutes after recovery of consciousness) or until the subject is ready for discharge. We will obtain approximately 15ml of blood (post-ketamine, pre-midazolam). The following computer presented neurocognitive assessment tests will also be performed: Global Precedence, Operation Span and Columbia Card tasks will also be administered (post-ketamine, pre-midazolam).

**E. Discharge:** If medically stable, as deemed by a board-certified anesthesiologist, the intravenous line and physiological monitoring devices will be discontinued, and subjects will be discharged home with a responsible family member or other adult caretaker. Discharge home will be based on criteria established by the MGH Department of Anesthesia practices for discharge from the hospital following ambulatory surgery. The subject must have stable vital signs, be able to respond appropriately to normal commands, be pain free, be free from any nausea and vomiting and have no bleeding from the intravenous sites. Subjects must be able to walk unassisted and have an accompanying adult to escort them home. Subjects will be advised against returning to work and driving or operating heavy equipment for 24 hours.

If subjects experience adverse events at home, they will be referred for evaluation at the nearest emergency department. These instructions will also be provided to the responsible adult escort prior to discharge. The subject's individual insurance plan will be responsible for covering this visit.

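### H1.2 calls the responsive gamma-stable state hallucinatory, but no planned analysis links that state to the hallucination ratings (CADSS)

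*Combined protocol and SAP*

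**What the plan says.** Section 2, Hypothesis 1.2, divides the gamma-stable pattern into an anesthetic state with zero response probability and "a hallucinatory state with non-zero probability of response to auditory stimuli". No other criterion for either state is given, and CADSS is not named there.

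Section 5 C describes the task: "Subjects will be asked to respond to auditory stimuli via button-press jittered at random between 4 and 8 second intervals". Its stated purpose is "in order to resolve the precise period at which loss and recovery of consciousness/responsiveness occurred at a fine temporal scale". No start or stop time is given.

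The Arrival part of Section 5 introduces CADSS as the instrument for assessing hallucinations. Section 5 D repeats it: "We will conduct assessments 5-minutes after recovery of consciousness and at approximately 15-minute intervals after recovery of consciousness for a total of three assessments". The listed content of those assessments is CADSS, PROMIS forms and cuff pain; the auditory task is not among them. After midazolam, "we will resume assessments for a minimum of two assessments (approximately 55 minutes after recovery of consciousness"), again without the task.

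Section 6 (Behavioral Analysis) fits a state-space model to the responses, aligned to each subject's loss of consciousness (LOC) and ROC and pooled for group estimates. Section 6 does not mention CADSS. The nearest use of a questionnaire is an exploratory correlation of blood analytes with variables of interest, for which pain and anxiety are named.

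**The concern.** Section 1 presents the relation between ketamine EEG and hallucinatory states as something earlier studies left open, and promises hallucination assessments to address it. H1.2 is where that question becomes a hypothesis. Yet the word *hallucinatory* in H1.2 rests on button presses alone, and the one instrument that could support it is collected but not analysed against EEG or responses.

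A button press shows that a subject is responsive. It does not show that the subject is hallucinating. If H1.2 is followed as worded, a responsive gamma-stable period would carry the hallucinatory label even where the subject's CADSS had returned to its arrival level. The report could then describe a hallucinatory brain state when the evidence shows only a responsive one.

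**Working it through.** **The plan's own figure.** The plan gives no figure on this point. Its only computed figure is the sample size in Section 6, which reproduces as a two-sided, two-group normal approximation: 2 × (1.960 + 1.282)² × 20² / 25² = 13.45, rounded up to 14. Nothing below depends on it.

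**The measures side by side.**

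| Element of H1.2 | Measured by | When (Section 5) | Planned analysis (Section 6) |
|---|---|---|---|
| Gamma-stable pattern | 64-channel EEG | Continuous; no stop time stated | Spectral and modal analyses; no rule for labelling a segment gamma-stable |
| Response probability | Button-press task | Described only in C; must reach ROC | State-space model, aligned to LOC and ROC |
| Hallucination | CADSS | Arrival; ROC + 5 min; about every 15 min to a total of three; at least two more after midazolam | None |

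**Timeline.** Inputs from Section 5: infusion about 5 minutes, unresponsiveness 10 to 15 minutes, period C nominally 15 minutes, first CADSS at ROC + 5. Assumptions: C starts with the infusion, and responsiveness is lost 0 to 5 minutes later.

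- ROC = onset + duration: earliest 0 + 10 = 10 min, latest 5 + 15 = 20 min.
- First post-ketamine CADSS = ROC + 5: 15 to 25 min.
- If the task stopped at the nominal end of C (15 min), it would end between 15 − 10 = 5 min after ROC and 20 − 15 = 5 min before it. It would end 15 − 15 = 0 to 25 − 15 = 10 min before that CADSS. It would not run alongside the rating, and in the later cases it would stop before ROC, contrary to its own purpose.
- If it ran to ROC + 5, the number of stimuli between ROC and the first CADSS would be 300 s divided by the interval: 300/6 = 50 at the mean interval of (4 + 8)/2 = 6 s, with a range of 300/8 = 37.5 to 300/4 = 75.
- The later pre-midazolam ratings fall at 5 + 15 = 20 and 20 + 15 = 35 min after ROC, the last agreeing with the figure in Section 5 D. No task is scheduled near either.

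The documents do not say which stopping time applies.

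**What each result would show.**

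| Gamma-stable EEG after ROC, with responses? | CADSS compared with arrival | H1.2 as worded | What the data support |
|---|---|---|---|
| Yes | Raised | Supported | Responsive state, with evidence of hallucination |
| Yes | Back at arrival level | Supported | Responsive state only |
| No | Either | Second state not found | Second state not found |

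The first two rows lead to the same conclusion under the plan, although they answer the hallucination question differently. CADSS, already collected, is what separates them.

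**The case against.** Several stronger readings are tempting, and the documents do not support them.

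- *The hallucinatory state is never observed.* The task must run to ROC to serve its purpose, it has no stop time, and Section 6 analyses ROC-aligned responses. Continuation to the first CADSS is neither scheduled nor excluded. A subject who answers CADSS or rates cuff pain is also overtly responsive, and EEG is described as continuous. What is missing in D is a scheduled response probability, not all evidence of responding.
- *The second limb of H1.2 is true by construction.* Responding after ROC does follow from how ROC is timed. Whether gamma-stable EEG persists past ROC does not. If the pattern ended at or before ROC, the second limb would fail, so it is testable.
- *The plan labels each epoch by whether a button was pressed.* It contains no such rule. It estimates probabilities by a state-space model and leaves classification unstated.
- *CADSS is a defining measure of H1.2.* H1.2 does not name it. The link is inferred from the purpose given to CADSS at arrival.
- *The anesthetic label contradicts the background.* Section 1 says "it is clear that unresponsiveness is not necessarily unconsciousness", but the same sentence goes on to value behavioral responses, and H1.2 does not use the word unconscious. This is an acknowledged limitation.

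The best remaining defence is that the first CADSS comes only 5 minutes after ROC and may be near enough. It is adjacent, and adjacency can be used, but only by an analysis that pairs the rating with nearby EEG and responses. None is planned. Two PROMIS forms are set to the past hour, while no recall period is stated for CADSS, so a raised first score could partly reflect the unresponsive period. The later ratings would help here, and the task is not scheduled near them.

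**Conclusion.** The point holds in this form: the plan can test whether gamma-stable EEG spans unresponsive and responsive periods around ROC, but it has no analysis showing that the responsive gamma-stable state is hallucinatory rather than simply responsive.

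The gap affects one limb of one hypothesis. Of the three pre-midazolam ratings, the first may have up to about 50 stimuli (38 to 75) in the preceding 5 minutes or none, depending on an unstated stop time. The other two have none scheduled. These counts describe the schedule. They do not measure information, because stimuli are clustered within at most 15 subjects.

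The conclusion rests on reading CADSS as the plan's measure of hallucination, which its stated purpose supports, and the timeline rests on the onset assumption above. If CADSS were not meant for this, H1.2 would have no measure of hallucination at all and its wording would still need to change. Sample size is unaffected.

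**What to change.** 1. **Section 6.** Add an analysis for H1.2 that compares gamma-stable EEG and response data next to each pre-midazolam CADSS rating with that rating's change from the subject's arrival score. Report responsive gamma-stable periods with CADSS at arrival level separately. State how a segment is classed as gamma-stable and what change in CADSS counts as raised. This uses data already planned and costs only text and analysis time.
2. **Section 5 C and D.** State the task's start and stop times. Continue it past ROC to the first CADSS, and run a block of about 2 minutes with EEG immediately before each of the next two pre-midazolam ratings: 120/6 = 20 stimuli per block (15 to 30 at intervals of 8 to 4 s). The cost is 2 × 2 = 4 extra minutes of task per subject, plus the continuation of up to 5 minutes after ROC, on equipment already in use. The downside is slightly longer assessments. The blocks make the measures adjacent rather than simultaneous, which is enough for the analysis in item 1. These data cannot be recovered once a visit is over.
3. **If neither is done,** reword H1.2 to unresponsive and responsive gamma-stable states. This costs nothing and matches what the present plan can show.

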**Behavioral Analysis:** The probability of response to verbal stimuli and the difference in probability of response will be estimated by using Bayesian Monte Carlo methods to fit a state-space model to these data. To perform group-level analyses, we will align the behavioral data across subjects with respect to each subject's LOC time for induction and with respect to each subject's ROC time for emergence. We will then pool the responses, and pooled data will be used to estimate group-level probabilities of response using the state-space model.

**Inflammatory profile Analysis:** Plasma samples will be submitted to Myriad/Rules Based Medicine (Myriad RBM, Austin, TX, USA) for analysis using their proprietary platform. Wilcoxon rank-sum tests with corrections for multiple comparisons will be used to assess analyte differences. In exploratory analyses, we will examine Pearson correlations between analytes and variables of interest (i.e. pain, anxiety).

**Power Analysis:** Assuming the point estimate for gamma power at baseline is -20 dB and 5 dB for ketamine induced-unconsciousness (**Fig 2.**), a standard deviation of 20 dB, type 1 error of 0.05, and desired power of 0.9,  $n=14$  study volunteers will enable us to detect a gamma power ratio of 25 dB. Therefore, we aim to recruit up to 15 subjects.

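### A one-hour recall period on the anxiety and positive-affect forms, repeated mostly every 15 minutes, makes the first post-ketamine score mostly pre-drug and dilutes later change.

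*Combined protocol and SAP*

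**What the plan says.** Section 5 applies the one-hour wording, "modified to ask for symptoms experienced within the past hour", to two forms. At arrival the anxiety form is the "Emotional Distress-Anxiety Short Form 8A modified to ask for symptoms experienced within the past hour", and the positive-affect form (15A) carries the same change. Part D (Recovery of consciousness) repeats both with that wording. The CADSS, the Meaning and Purpose form and the pain forms have no stated one-hour window.

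The schedule after recovery of consciousness (ROC) is: "We will conduct assessments 5-minutes after recovery of consciousness and at approximately 15-minute intervals after recovery of consciousness for a total of three assessments". Midazolam comes next: "After the third assessment (i.e. approximately 35 minutes after recovery of consciousness), we will administer" it. Then: "Approximately 5 minutes after midazolam is administered, we will resume assessments for a minimum of two assessments". The second of these is placed at about 55 minutes after ROC, and assessments may continue until discharge.

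On drug timing, part C says "2mg/kg of ketamine will be infused (Medfusion pump) over approximately 5 minutes" and "This anesthetic dose is expected to cause approximately 10-15 minutes of loss of consciousness/responsiveness".

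On use of the scores, the Background lists anxiety, with hallucinations and pain, among the things to be assessed. Section 6 (Inflammatory profile Analysis) plans exploratory Pearson correlations between analytes and "variables of interest (i.e. pain, anxiety"). No hypothesis in section 2 concerns anxiety, affect or midazolam.

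**The concern.** A repeated self-report can follow change only if each administration refers mainly to the time since the previous one. Here the recall period is four times the usual spacing. A subject answering five minutes after waking is asked about an hour that is mostly baseline and arrival. That period includes placing the intravenous line and raising the cuff stimulus to a pain rating of 8-9 out of 10, so distress from those procedures could be scored as post-ketamine anxiety. In part D the cuff is inflated after the questionnaires, so each later one-hour window also takes in the cuff pain of earlier assessments.

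At stake is whether the five post-ketamine scores on these two forms can be read as states at five times. Later analysis cannot separate the minutes that a subject merged into one answer.

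**Working it through.** **Inputs from section 5.** Recall window 60 min. Assessments at ROC+5, +20 and +35 min. Midazolam at about ROC+35. Assessments resume 5 min later. Loss of consciousness 10-15 min. Infusion about 5 min.

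**Assumption.** The time from start of infusion to loss of consciousness is not given. I take 0-5 min, so the time from start of infusion to ROC is T = 0+10 to 5+15 = 10-20 min.

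**The plan's own times.** 5 + 15 + 15 = 35, and 35 + 5 + 15 = 55. Both agree with the stated 35 and 55 min, and the first post-midazolam assessment falls at 35 + 5 = 40 min.

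**Overlap.** Window over spacing = 60/15 = 4. Windows 15 min apart share 60 − 15 = 45 of 60 min (75%). The windows at ROC+35 and ROC+40 share 55 of 60 min (92%).

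**Pre-drug share** at ROC+a = max(0, 60 − (T + a))/60. **Post-midazolam share** = max(0, a − 35)/60.

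| Assessment | Pre-drug minutes (T = 20 to 10) | Pre-drug share | Post-midazolam share |
|---|---|---|---|
| ROC+5 | 35-45 | 58-75% | 0% |
| ROC+20 | 20-30 | 33-50% | 0% |
| ROC+35 | 5-15 | 8-25% | 0% |
| ROC+40 | 0-10 | 0-17% | 5/60 = 8% |
| ROC+55 | 0 | 0% | 20/60 = 33% |

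**Sensitivity to T.** The ROC+5 window is mostly pre-drug when 60 − (T + 5) > 30, that is, when T < 25 min. This covers the whole assumed range.

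**Conscious time only.** A subject cannot report on unconscious minutes. Removing 10-15 min from the denominator gives, at ROC+5, 45/50 = 90% down to 35/45 = 78%. At ROC+20 it gives 30/50 = 60% down to 20/45 = 44%, and at ROC+35 15/50 = 30% down to 5/45 = 11%.

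**Reach into arrival.** At ROC+5 the window begins 35-45 min before infusion. If a baseline of 10-15 min runs directly up to infusion, the window takes in 35 − 15 = 20 to 45 − 10 = 35 min of an arrival period of about 45 min. The documents do not give the order and timing within arrival, so how much of the cuff titration falls inside is not known exactly.

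**Effect on a score.** If answers average evenly over the hour, a step change D at the start of ketamine shows as 1 − 0.75 = 0.25 D to 1 − 0.58 = 0.42 D at ROC+5. A step at midazolam shows as 0.08 D at ROC+40 and 0.33 D at ROC+55.

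**With a short window.** For a 'right now' item, represented by at most 5 min, the pre-drug share is 0% at all five times and the post-midazolam share is 100% at ROC+40 and ROC+55.

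**With 'since the last assessment'.** At ROC+5 this reaches back to the arrival forms. Let G be the gap from those forms to infusion, assumed 45-60 min from an arrival of about 45 min and a baseline of about 15 min. The pre-drug share is G/(G + T + 5), which runs from 45/(45 + 20 + 5) = 64% to 60/(60 + 10 + 5) = 80%. That is no better than now.

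**The case against.** The strongest case against is that little in the plan depends on these scores. No hypothesis concerns anxiety, affect or midazolam, and section 6 describes no time-course analysis of the two forms. The only named use of anxiety is exploratory. The documents do not say which anxiety score is paired with the post-ketamine, pre-midazolam blood sample; if it is the ROC+35 score, the pre-drug share is 8-25%. A Pearson correlation is also unchanged by uniform scaling, so dilution would matter there only through the extra pre-drug variation, which cannot be sized from the documents. All of this stands, and it limits the impact.

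Even weighting is also an assumption. A recent strong symptom might be reported in full whatever the window. That stands too, but it does not rescue the form: the period a score describes would then be unknown.

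A reader might infer that all the early scores are mostly pre-drug. In clock time that holds only at ROC+5; at ROC+20 the share is at most 50%, and at ROC+35 at most 25%. A reader might also infer that a midazolam effect cannot be seen. Under even weighting a third of it shows at ROC+55, and two post-midazolam assessments are only the minimum. If they continue towards discharge, half the window follows midazolam by ROC+65 (30/60).

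Nor do the documents support saying that midazolam would look ineffective for its stated purpose. It is given for perceptual disturbances, and the CADSS, the instrument named for hallucinations, has no stated one-hour window.

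**Conclusion.** The point holds for two forms. The 75% overlap and the 8% and 33% post-midazolam shares follow from the stated schedule, with 15-minute spacing carried past midazolam. The 58-75% pre-drug share at ROC+5 rests on 10-20 min from start of infusion to recovery, and remains a majority up to 25 min. Attenuation of the scores rests further on roughly even weighting of the hour.

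The consequence is poorer data on anxiety, which the Background names for assessment, and on positive affect. It does not threaten any hypothesis, the CADSS or the pain measures. This is a worthwhile, inexpensive improvement rather than a fault in the main analyses.

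**What to change.** Change the recall wording of the anxiety and positive-affect forms to 'right now' at every administration, including arrival, so that baseline and follow-up refer to the same kind of period. Leave the assessment schedule unchanged. Do not use 'since the last assessment': at ROC+5 it reaches back to arrival, and it gives each administration a different recall length.

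The cost is one phrase on two forms that are already modified, with no change to subject burden, sample size or procedures. The downside is real but small: symptoms that arose and resolved before an assessment, such as distress during induction or emergence that ended before ROC+5, are no longer captured by these two forms.
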